### **9.10. Other aspects**

Insofar as no additional examination will be performed compared to the usual management of patients with CML, the medical services provided and the medicinal products prescribed will be reimbursed by the social security system. The fixed reimbursement is paid in the capacity of work load invested in the documentation and completion of the study questionnaires.

## **10. PROTECTION OF PATIENTS**

### **10.1. Information leaflet for patients**

All parties will comply with legislation in force, in particular laws concerning the implementation of organizational and technical measures designed to ensure the protection of patients' personal data. These measures will include omission of the names of patients or of other data enabling to identify them directly in all reports, all publications and all other disclosures, except for requirements imposed by legislation in force.

Personal data will be kept in the study centre in encrypted electronic or paper format and will be protected by a password or secured in a locking room in order to ensure that only study certified staff can have access to it. The study centre will set up appropriate technical and organizational measures in order to ensure that personal data can be recovered in the eventual case of an accident. In the eventuality of potential violation of personal data, the study centre will assume responsibility to determine if this violation was really produced and, in this case, to carry out the notifications required by law.

In order to protect the rights and freedoms of physical persons with respect to the processing of personal data, when study data are compiled in order to be transferred to Pfizer and to other certified parties, patients' names will be removed and replaced by a unique specific code number, based on a numbering system defined by Pfizer. All other data enabling identification of patients which will be transferred to Pfizer or to other certified parties will be identified by a specific unique code for each patient. The participating doctor's centre will keep a confidential list of patients who participated in the study, with a link between the numerical codes of each patient and the real identity of each of them. In case of transfer of data, Pfizer will maintain high standards of confidentiality and protection of patients' personal data in conformity with conditions of the study contract and laws in force on protection of private life.

## **10.2. Consent of patients**

Informed consent documents and all materials intended for recruitment of patients must comply with regulatory and local legislative requirements, in particular laws in force on respect of private life.

Informed consent documents used in the process for obtaining informed consent and all materials enabling recruitment of patients must be examined and approved by Pfizer, approved by the ethics committee (CPP – Committee for Protection of Persons)/independent ethics committee (IEC) with their use, and must be available for inspection.

The participating doctor must ensure that all patients in the study are fully informed about the nature and objectives of the study, on communication of data relating to the study, and on possible risks associated with their participation, in particular risks associated with the processing of personal data of patients. The participating doctor must also make certain that all patients in the study have been fully informed of their rights of access and correction of their personal data, and of withdrawal of their consent for processing of their personal data.

## **10.3. Withdrawal of a patient**

Patients can withdraw from the study at any time at their own request or may be withdrawn at any time based on the judgement of the participating doctor or the sponsor for reasons of safety of use, behavior or administrative reasons. In all circumstances, every effort must be made to document the outcome of the patient whenever applicable. The participating doctor will collect information on the reason for a patient's withdrawal and follow-up with the patient, concerning all unresolved adverse events.

If a patient withdraws from the study and also withdraws his consent for disclosure of future information, no other evaluation should be made and no other data should be collected. The sponsor can keep and continue to use all data collected before the withdrawal of consent.

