
NATURE AND DURATION OF STUDY
	
This is a national, observational, descriptive, prospective, multi-centre study conducted in Metropolitan France in adult patients treated for chronic phase, accelerated or blast phase Philadelphia chromosome positive (Ph+/-) CML, previously treated with one or more TKIs and for whom imatinib, dasatinib or nilotinib are not considered as appropriate treatments. The study will be conducted in all centres involved in management of CML, i.e. about twenty (20) centres are expected.
 
The study will be offered to all patients who satisfy criteria for eligibility up to the end of the recruitment period. Eligible patients but not included in the study will be recorded in a non-inclusion registry.
 
Patients will be followed prospectively throughout the duration of the study (3-year follow-up) starting from their inclusion in the study. Follow-up data will be collected at follow-up visits conducted in the setting of usual management, estimated at every 3 months independently of discontinuations, changes or discontinuations of treatment possibly implemented. Therapeutic management of the patient will not be

	
changed by participation in the study.

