### **9.1. Study design**

This is a national, observational, descriptive, prospective, multicentre study conducted in metropolitan France in adult patients treated for accelerated or blast phase Philadelphia chromosome positive chronic myeloid leukemia, previously treated with one or more TKIs and for whom imatinib, nilotinib and dasatinib are not considered as appropriate treatments. The study will be conducted in all centres involved in management of CML, i.e. about twenty (20) in expected centres.

[figure not shown]
The study will be offered to the totality of patients who satisfy criteria for inclusion and for non-inclusion up to the end of the inclusion period defined as 4 years. About one hundred

(100) patients included are expected in the study. Therapeutic management of a patient will not be changed by participation in the study and will depend on decisions taken by doctors in agreement with current international recommendations (European Leukemia Net, ELN network [13]) (see paragraph 7.3).

Patients will be followed prospectively over a 3-year period starting with their inclusion in the study. The inclusion visit will be performed at time of inclusion of the patient in the study, after which the patient has been informed and has accepted to participate by signing the consent form. Follow-up visits will be performed after usual consultation, estimated at about every 3 months. No visit or additional examination will be requested by the protocol: modalities for follow-up and treatment will be left up to the entire judgement of the participating doctor. Data will be recorded during the 3 years of the patient's participation, except in case of withdrawal of consent, death of a patient or termination of the study before its planned end.

Total duration of the study is estimated at 7 years with an inclusion period of 4 years and a follow-up period of 3 years (see Figure 1). Throughout the study, at least one monitoring visit per year will be performed.

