#### 9.4.1.3. Long-term follow-up visit

Patients who have permanently discontinued their treatment with bosutinib will be followed according to their usual management, estimated at every 3 months in conformity with recommendations of management of CML. Doctors will complete *via* eCRF a long-term follow-up visit for all these patients.

At this visit, the following information will be provided:

- Outcome of the CML Phase
- Therapeutic management of CML

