#### Abnormal test results

The criteria enabling to determine if abnormal test data in an objective test should be reported as an adverse event are as follows:

- The test result is associated with symptoms, and/or
- The test result requires additional diagnostic investigations or a medical/surgical intervention, and/or
- The test result leads to a change to dosage or withdrawal of the patient from the study, to administration of a significant additional concomitant treatment or another treatment, and/or
- The test result is considered as an adverse event by the participating doctor or the sponsor.

The simple repetition of an abnormal test, in the absence of the aforementioned conditions, does not constitute an adverse event. Any abnormal test result which proves to result from an error does not need to be reported as an adverse event.

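### Section 10.3 lets the doctor or sponsor withdraw a patient from this observational safety study on safety grounds, an avoidable route to outcome-dependent loss that does not fit the exit rules in 9.1, 9.4.1.3 and 9.4.1.4

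*Protocol*

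**What the plan says.** Section 10.3 covers withdrawal from the study. Apart from the patient's own request, it provides that patients "may be withdrawn at any time based on the judgement of the participating doctor or the sponsor for reasons of safety of use, behavior". Administrative grounds are allowed as well. The same section adds safeguards. "In all circumstances, every effort must be made to document the outcome of the patient whenever applicable", and the doctor is to collect the reason and "follow-up with the patient, concerning all unresolved adverse events". It also says that "The sponsor can keep and continue to use all data collected before the withdrawal of consent".

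Other sections describe who stays under observation:

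- **9.1** records data over the patient's 3 years "except in case of withdrawal of consent, death of a patient or termination of the study before its planned end".
- **9.4.1.3** states: "Patients who have permanently discontinued their treatment with bosutinib will be followed according to their usual management". Doctors complete a long-term follow-up visit for all of them.
- **9.4.1.4** requires an end-of-study visit for every patient who leaves before 36 months. Its parenthesis names loss to follow-up, death and withdrawn consent. Withdrawal by the doctor or sponsor is not named.
- **4 (Synopsis)** keeps follow-up going "independently of discontinuations, changes or discontinuations of treatment possibly implemented".
- **11.5.1 (Abnormal test results)** lists, among the triggers for reporting a result as an AE: "The test result leads to a change to dosage or withdrawal of the patient from the study".

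The primary objectives (8.1, 9.7.2) are the percentage of patients with bosutinib-related AEs, overall, by grade and by type, and the percentage who permanently discontinue bosutinib after a related AE.

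**The concern.** In an interventional trial, a safety withdrawal takes the patient off an assigned treatment. Here, 9.1 and 10.4 leave treatment to routine care, so leaving the study changes nothing for the patient except that data stop. A safety ground for leaving therefore has no protective purpose.

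It does have a statistical cost. Toxicity is the subject of both primary endpoints, so a patient's chance of being lost could depend on the outcome being measured. A patient withdrawn during a temporary interruption could later stop for good without being counted in the second primary endpoint. In the Kaplan-Meier analyses of PFS and OS (9.7.3), such a patient would be censored at or near a toxicity event, and the method treats that censoring as unrelated to prognosis.

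The sections also give a site no consistent instruction. A doctor using the power in 10.3 ends data recording for a reason that 9.1 does not list.

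**Working it through.** **1. Does the clause fit the other sections?**

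| Section | What ends or continues observation | Withdrawal by doctor or sponsor |
|---|---|---|
| 9.1 | Ends for withdrawn consent, death, study termination | Not listed |
| 9.4.1.3 | Continues after a permanent stop of bosutinib | Not foreseen |
| 9.4.1.4 | End-of-study visit for all early exits; three types named | Within the general wording, not named |
| 10.3 | Doctor or sponsor may end it, including on safety grounds | Allowed |

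Section 10.3 is the outlier.

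**2. What is still captured after such a withdrawal?**

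- The triggering AE: normally already in the eCRF.
- Unresolved AEs: followed under 10.3. Related AEs: followed to resolution or stabilisation under 11.4.
- Related SAEs of which the doctor becomes aware: reportable after the observation period (11.3).
- Bosutinib status, vital status and last known responses: collected at end of study (9.3), on the form that 9.4.1.4 requires for all early exits.

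**3. What can be lost?**

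- A permanent discontinuation decided after exit.
- New non-serious related AEs after exit.
- Later progression, transformation and death, beyond what best-effort outcome documentation recovers.

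**4. The plan's own precision figure.** Section 9.5 gives a 95% half-width of at most 10% for 100 patients at a 50% rate (Wald):

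1.96 × √(0.5 × 0.5 / 100) = 0.0980, or 9.8 points. The figure reproduces.

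The smallest n that keeps it is (1.96 / 0.10)² × 0.25 = 96.04, so 97 patients. If 5, 10 or 20 patients fell out of the denominator, the half-width would be 10.05, 10.33 or 10.96 points. Precision is hardly affected, so the issue is bias.

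**5. Illustration for the second primary endpoint.** Inputs: 100 patients (9.5), and about 20% permanently stopping after an AE in the earlier single-arm trial (7.3), so 20 true stops. That 20% covers any AE, not only related ones, so it is a stand-in. The number *m* of stops missed because the patient had already been withdrawn is assumed.

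| *m* | Counted as non-events, (20 − *m*)/100 | Dropped, (20 − *m*)/(100 − *m*) |
|---|---|---|
| 2 | 18.0% | 18.4% |
| 5 | 15.0% | 15.8% |
| 10 | 10.0% | 11.1% |

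With *m* = 2 the relative error is 2/20 = 10%. The sampling half-width at 20% is 1.96 × √(0.2 × 0.8 / 100) = 7.8 points, so an error of 2 points lies well inside it.

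**The case against.** The strongest defence is that the protocol already recovers most of what matters. The end-of-study form applies to every early exit and records bosutinib status and vital status. Related AEs are followed to resolution, and related SAEs remain reportable. Section 9.1 does not call its list exhaustive and also omits loss to follow-up, which 9.4.1.4 and 9.9.3 treat as an exit. Section 9.9.3 compares completers with patients who left early, so a differential pattern could be seen.

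Much of this stands, and it rules out several stronger readings that a reader might infer:

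- *That toxicity disappears from the first primary endpoint.* It does not. The triggering AE is recorded and followed.
- *That the synopsis contradicts 10.3.* Its sentence is about changes of treatment, not exit from the study.
- *That 11.5.1 gives a second power to withdraw.* It only says when a test result must be reported as an AE.
- *That survival is overstated by a definable amount.* Any figure needs a mortality rate, a hazard after stopping and a fraction withdrawn. The protocol gives none of these, and 9.4.1.3 sends permanent stoppers to long-term follow-up by default.
- *That every error favours bosutinib.* A missed stop lowers the discontinuation rate, but the direction for PFS and OS depends on how withdrawn patients fare afterwards.

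The defence does not remove the remaining gap. Outcome documentation is best-effort and does not continue the roughly 3-monthly collection. The form shows status at exit, not a stop decided later. The comparison in 9.9.3 can reveal selective loss but cannot recover the data.

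**Conclusion.** The point holds in a limited form. Section 10.3 permits withdrawal from observation for a reason that overlaps both primary endpoints, serves no protective purpose in a non-interventional study, and does not fit 9.1, 9.4.1.3 or 9.4.1.4. The percentage with any related AE is little affected. Exposed are the permanent-discontinuation endpoint (stops decided after exit), counts of later non-serious related AEs, and PFS and OS through informative censoring.

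The size cannot be derived, because no expected rate of withdrawal by doctor or sponsor is stated. The move from 20% to 18% assumes two missed stops and a rate borrowed from an endpoint that is not restricted to related AEs. It is smaller than the sampling error at n = 100, but unlike sampling error it can be avoided by wording alone. The change should be made.

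**What to change.** - **10.3:** remove safety of use as a ground on which the doctor or sponsor may withdraw a patient from the study. State that stopping bosutinib is not leaving the study, and that patients who stop permanently continue under 9.4.1.3.
- **9.1, 9.4.1.4 and 10.3:** use one common list of exits, including loss to follow-up. Record any remaining withdrawal by doctor or sponsor with its reason, and name it among the exits covered by the end-of-study form.
- **11.5.1 (Abnormal test results):** keep the existing reporting trigger and add discontinuation of bosutinib to it. Replacing the present words would remove one route by which an abnormal result becomes a reportable AE.

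The cost is a wording amendment and, if the end-of-study form lacks it, one extra exit category. No visits are added, because follow-up uses routine consultations, and no treatment rule changes.

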## **10.4. Committee for Protection of Persons (CPP)/Public Health Code Law no. “2004-806 of 9 August 2004”**

This trial is an observational study that does not in any way modify the usual medical management of persons entering the study, and does not harm the physical or psychological integrity and does not require a specific follow-up visit for persons entering the study. All procedures are performed and products used in the usual manner with no unusual or additional diagnostic or monitoring procedure.

Under these conditions, the study does not fall within the scope of application of law of program no. 2006-450 of 18 April 2006 for research nor law no. 2004-806 of 9 August 2004 article 88 chapter II article L1121-1 and therefore the project is not subject to submission to the National Agency for Medicines and Health Products Safety (ANSM), nor to a Committee for Protection for Persons (CPP) (ethics committee).

Regulation no. 2016-800 of 16 June 2016 relating to research involving a human person stipulates in its article 8 that research regularly reported or authorized at date of entry in force of the application decision (application decision of the so-called Jardé law no. 2016-1537 of 16 November 2016) continues in force during five years in compliance with legislation which was initially applicable to them.

At the end of this 5-year period, it will be submitted to another examination by the Ethics Committee and, if applicable, by the National Agency for Medicines and Health Products Safety under conditions stipulated by the Public Health Code.

In this regard, for an opinion which has been issued prior to 16 November 2017, the Ethics Committee is not competent for substantial changes on this project.

### **10.5. National Medical Council**

Participating doctors and experts in the scientific committee will be compensated for their participation in the study. The study protocol and the financial agreements will be submitted to the National Medical Council (article L4113-6 of the Public Health Code and articles R4113-104 and R4113-105).

Each participating doctor and scientific expert must send to the National Medical Council a copy of his/her contract (articles L4113-9, L4113-10 and L4163-10 of the Public Health Code).

### **10.6. Ethical conduct of the study Protection of Data: National Committee on Data Processing and Freedoms “CNIL”**

In compliance with law 78-17 of 6 January 1978 relating to data processing, computer files and freedoms, as modified by law 2004-801 of 6 August 2004 relating to protection of physical persons with regard to processing of personal data, this protocol has been submitted in a request for an opinion from the Consultative Committee on Data Processing in the Area of Research in the Field of Health (CCTIRS). Upon receipt of a favorable opinion from this committee, the computer file used to write the present study has been the subject of a request for authorization from the National Committee for Data Processing and Freedoms (CNIL). This computer file can be used only after receipt of authorization from the CNIL.

Since this involves the potential competence of the Consultative Committee on Data Processing in the Area of Research in the Field of Health (CCTIRS) which has been eliminated on 5 May 2017, date of a decision concerning creation of the Expert Committee on Research, Studies and Evaluations in the Field of Health (CEREES) in application of French law no. 2016-41 of modernization of the health system of 26 January 2016, and of the application decision of the so-called Jardé law no. 2016-1537 of 16 November 2016, the departments of the ministry of research are no longer competent for analysis of corrections made to research projects.

Also, in compliance with law 78-17 of 6 January 1978 relating to data processing, files and freedoms modified by law 2004-801 of 6 August 2004 relating to protection of physical persons regarding processing of personal data, the protocol has been submitted in a request for authorization from the National Commission on Data Processing and Freedoms (CNIL). This computer file may be implemented only after receipt of authorization from CNIL.

### **10.7. Ethical conduct of study**

The study will be conducted in compliance with legislative and regulatory requirements, in conformity with its objective, scientific value and rigorousness and will follow the practices of research generally accepted and described in the following documents:

- Recommendations on Good Pharmacoepidemiologic Practice (GPP) published by International Society for Pharmacoepidemiology (ISPE),  
[https://www.pharmacoepi.org/resources/guidelines\\_08027.cfm](https://www.pharmacoepi.org/resources/guidelines_08027.cfm)
- Recommendations on Good Epidemiological Practice (GEP) published by the International Epidemiological Association (IEA),  
<http://ieaweb.org/2010/04/good-epidemiological-practice-gep/>
- Good practice of research on results on results published by the International Society for Pharmacoepidemiology and Outcomes Research (ISPOR),  
[http://www.ispor.org/workpaper/practices\\_index.asp](http://www.ispor.org/workpaper/practices_index.asp)
- Recommendations on Good Practice for studies on health data under real life conditions concerning a treatment and/or comparative efficacy: recommendations of the joint working group ISPOR-ISPE on concrete evidence in decision making in the area of healthcare  
<https://www.ncbi.nlm.nih.gov/pmc/articles/PMC5639372/>
- International ethical recommendations for epidemiological research published by the Council for International Organizations of Medical Sciences (CIOMS)  
<http://ieaweb.org/wp-content/uploads/2012/06/cioms.pdf>
- European Medicines Agency (EMA) European Network of Centres for Pharmacoepidemiology and Pharmacovigilance (ENCePP) Guide on Methodological Standards in Pharmacoepidemiology
- The ENCePP Code of Conduct for scientific independence and transparency in conduct of studies of pharmacoepidemiology and pharmacovigilance  
[http://www.encepp.eu/code\\_of\\_conduct/documents/ENCePPCodeofConduct\\_Rev3.pdf](http://www.encepp.eu/code_of_conduct/documents/ENCePPCodeofConduct_Rev3.pdf)
- Guide of methodological standards in pharmacoepidemiology, guidelines of the Food and Drug Administration (FDA) for industry: Good Practice of pharmacovigilance and of pharmacoepidemiologic evaluation (Good Pharmacovigilance and

Pharmacoeconomic Assessment),

<https://www.fda.gov/downloads/drugs/guidancecomplianceregulatoryinformation/guidances/ucm071696.pdf>

- FDA guidelines for industry and FDA staff: Good Practice of conduct and reporting of pharmacoeconomic studies of safety using all electronic medical data  
<http://www.fda.gov/downloads/Drugs/GuidanceComplianceRegulatoryInformation/Guidances/UCM243537.pdf>
- Guidelines for industry: Measures evolution recorded by the patient: Use in development of medical products to support labelling of the label.  
<http://www.fda.gov/downloads/Drugs/Guidances/UCM193282.pdf>

